### 3.3.2 Secondary Endpoints

**Objective:** To demonstrate impact of acupuncture on BCG adherence on direct and indirect measures that include evaluation of BCG protocol experience, patient-reported outcomes of overall quality of life and urinary symptoms, and quantification of medication usage for symptom management.

Analysis plan:

1. Compare Rates of BCG instillation adherence (out of a possible planned six treatments), treatment interruptions, weeks missed, intravesical BCG dwell times (as measured in minutes), and requirement for dose reductions between the acupuncture and control arms.
2. Compare the responses of patients in the experimental and control arms to the EORTC-QLQ-NMIBC-24 symptom index, which was specifically designed to assess bladder and bowel symptoms for patients with NMIBC including assessments of impact of intravesical therapy, and the EORTC-QLQ-C30 , which assesses general quality of life. These assessments will be compared between patients by week of treatment (from week 1 to week 6).
3. Median weekly pill counts standardized by dosage across medication types will be compared between the experimental and control arms by week of therapy. Patients will be given a weekly medication diary and asked to record the number of pills/doses taken per day of specific medications which are administered for bladder symptom management while undergoing intravesical therapies. This pill diary will include topical analgesics such as phenazopyridine, anticholinergic medications, Beta-3 adrenergic receptor agonists (e.g. mirabegron), systemic pain medications including acetaminophen, nonsteroidal anti-inflammatory agents, narcotics, and other naturopathic therapies targeted at symptoms of dysuria, bladders spasms, and pelvic pain.

**Expected results and interpretation:** We hypothesize that patients in the experimental group will have higher proportion finishing BCG regimen, with less interruptions and fewer required dose reductions of BCG. We hypothesize that patients in the experimental group will report similar general quality of life and NMIBC-specific symptoms initially. However, as patients advance in their treatments from 1 to 6 weeks, we anticipate that patients in the experimental arm will endorse improved quality of life and lower levels of bladder/bowel symptoms compared to the control arm. Furthermore, we predict that patients randomized to the experimental arm will have higher rates of protocol retention, treatment adherence, and median intravesical dwell times of the BCG at each treatment. We hypothesize that patients in the experimental arm will report taking lower amounts of adjunctive medications for bladder-related symptoms and that the discrepancy in adjunctive treatments taken will increase across the 6 weeks of therapy as the BCG-related symptoms are expected to increase with each subsequent intravesical dose of BCG.

### **3.4 Estimated Accrual**

The University of Washington Medical Center (UWMC) Department of Urology Clinic administers BCG to high-risk NMIBC patients receiving either induction or maintenance therapy approximately 40-50 times monthly. We will recruit 45 BCG-adults from the UWMC Department of Urology who are scheduled to receive 6 weekly doses of intravesical BCG.

### **3.5 Name of Sponsor/Funding Source**

Sponsor: Early Phase Clinical Research Support Application, Cancer Center Support Grant

Award ID# P30 CA015704-44

## **4.0 SAFETY CONSIDERATIONS**

### **4.1 Stopping Rules**

This trial does not contain stopping rules.

Patients will be monitored for BCG-related toxicity as per standard of care practice. Modifications to BCG dosing and intervals between treatment will be made on a per-patient basis per usual care.

## **5.0 SUBJECT ELIGIBILITY**

### **5.1 Inclusion Criteria**

#### **5.1.1 Demographic Data**

- 1) 18 years of age or older
- 2) English-speaking

#### **5.1.2 Disease Related Criteria**

- 3) Diagnosis of American Urological Association (AUA) high-risk NMIBC, including high grade (HG) pT1 (invading only the lamina propria of the bladder), recurrent HG pTa (superficial tumors), HG pTa >3cm in size or multifocal, any carcinoma in situ, any variant histology, any lymphovascular invasion, and HG prostatic urethral involvement(3)
- 4) Diagnosis with urothelial carcinoma (primary histologic subtype), localized to the bladder, in the absence of nodal or other visceral metastases.
- 5) Patients who have been indicated for induction intravesical BCG in shared-decision-making with their primary urologist.

#### **5.1.3 Prior/Current Related Criteria**

- 6) Have not received acupuncture in the previous 3 months.

#### **5.1.4 Accessibility Criteria**

- 7) Access to phone for study contacts.
- 8) Willing and able to participate in trial activities

#### **5.1.5 Clinical/Laboratory Criteria**

- 9) Platelets: 20,000/  $\mu$ L or greater
- 10) ANC: 500 cells/ $\mu$ L or greater

#### **5.1.6 Ability to understand and the willingness to sign a written informed consent document.**

- 11) Able to understand and willing to sign written informed consent in English.

### **5.2 Exclusion Criteria**

#### **5.2.1 Receipt of prior therapy**

Subjects who have had intravesical or systemic chemotherapy or radiation therapy for bladder cancer or for other malignancies prior to entering the study.

**5.2.2 Subjects may not be receiving other investigational agents or other combined intravesical therapies.**

Subjects who are indicated to receive other intravesical agents or therapies concurrently with BCG will be excluded.

**5.2.3 Disease-specific criteria**

Subjects who have muscle-invasive bladder cancer, radiographic evidence of lymph node metastases or metastatic disease involving other organs including brain metastases.

Patients with predominant histology other than urothelial carcinoma of the bladder who would not otherwise be considered candidates for BCG.

**5.2.4 Contraindications to receiving intravesical BCG**

BCG is contraindicated in:

- Patients who are pregnant or lactating
- Patients with active tuberculosis
- Immunosuppressed patients with congenital or acquired immune deficiency, whether due to concurrent disease (e.g. AIDS, Lymphoma, Leukemia), concomitant cancer therapy (cytotoxic drugs, radiation), or immunosuppressive therapy (e.g. corticosteroids, DMARDs).
- Symptomatic urinary tract infection
- Febrile illness
- Patients requiring chronic treatment with certain antibiotics that may interfere with the effectiveness of BCG.
- Any previous allergies or severe reactions to BCG

**5.2.5 Contraindications to Acupuncture/Electrostimulation**

- Not pregnant or trying to become pregnant. Acupuncture points included in the protocol are contraindicated with pregnancy.
- Does not have a pacemaker. There is potential of electrostimulation interfering with the operation and function of pacemakers.

**5.2.6 Address concomitant medications which may have an effect on the pharmacokinetics of the investigational agent.**

- Patients requiring chronic treatment with certain antibiotics that may interfere with the effectiveness of BCG. Fluoroquinolone therapy may decrease the efficacy of intravesical BCG. Antibiotic therapy for ongoing treatment of active tuberculosis will decrease the efficacy of intravesical BCG.

**5.2.7 Uncontrolled or concurrent illness including, but not limited to, ongoing or active infection, symptomatic congestive heart failure, unstable angina pectoris, cardiac arrhythmia, or psychiatric illness/social situations that would limit compliance with study requirements.**

**5.2.8 Address excluding pregnant women from the study.**

- 1) Pregnant women are excluded. Acupuncture points included in the protocol are contraindicated with pregnancy and BCG is contraindicated in pregnancy.

**5.2.9 Any additional exclusion criteria and the rationale.**

- 2) Pacemaker. Patients with pacemakers are restricted due to the potential of electrostimulation interfering with a pacemakers operation.
- 3) Platelets: < 20,000/ µL. Risk of bleeding with acupuncture
- 4) ANC: < 500 cells/µL. Risk of infection with acupuncture
- 5) Received acupuncture in the previous 3 months. Acupuncture treatment effects persist after a course of treatment, previous exposure to the intervention has the potential to affect the baseline data for treatment and control arms.(25)

**6.0 SUBJECT REGISTRATION**

Subjects will be registered by the Fred Hutch/UW Study Coordinator and entered into the OnCore CTMS. A complete, signed, study consent and HIPAA consent are required for registration.

[figure not shown]
**7.0 TREATMENT PLAN**

Briefly outline the major treatment components of this protocol including treatment agents, timing and method of administration, setting of administration (inpatient or outpatient), duration of therapy and anticipated toxicities and the method of treatment of these toxicities. Also address the administration of prophylactic or supportive care drugs or regimens and any interactions with the study agent that prohibit the administration of specific concomitant medications.

For those evaluations or procedures that are somewhat flexible in reference to timing, allow for flexibility by stating in the protocol that they may be done “plus or minus” x days. This will further ensure compliance with the protocol.

Outline Treatment Schedule	
Day	Treatment
1 +/- 7	Acupuncture Treatment #1 BCG Instillation #1
8 +/- 7	Acupuncture Treatment #2 BCG Instillation #3
15 +/- 7	Acupuncture Treatment #3 BCG Instillation #3
22 +/- 7	Acupuncture Treatment #4 BCG Instillation #4
29 +/- 7	Acupuncture Treatment #5 BCG Instillation #5
36 +/- 7	Acupuncture Treatment #6 BCG Instillation #6

**7.1 Treatment Plan Overview****SCHEMA**

## 7.2 Waitlist Control

At the end of the study, participants randomized to the waitlist control group will receive 4 coupons to receive free acupuncture in the Prevention Center at the Fred Hutchinson Cancer Research Center.

## 7.3 Concomitant Medication, Interruption of Therapy, and Supportive Care Guidelines

- A urine analysis will be performed prior to instillation. If bacturia is present on high power field or >5 WBCs are present on high power field and/or gross hematuria is noted and/or the patient complains of acute cystitis symptoms (urinary urgency, frequency, dysuria), instillation is deferred and urine is sent for culture to confirm the presence of UTI and sensitivity to culture. Appropriate antibiotic therapy is prescribed per standard of care clinical practice. Findings are discussed with the prescribing clinician. Microscopic hematuria only or isolated WBCs in an otherwise asymptomatic patient do not preclude treatment.
- For patients complaining of bladder spasms, urinary urgency, or frequency: anticholinergic medications such as oxybutynin, tolterodine, darifenacin, solifenacina, trospium, fesoterodine or Beta-3 adrenergic agonists such as mirabegron will be prescribed. For severe refractory bladder spasms, other medications such as benzodiazepines, may be used to relax the bladder.
- For male patients complaining of obstructive urinary symptoms: alpha-antagonists such as tamsulosin may be used.
- For patients complaining of bladder pain, local analgesics such as phenazopyridine may be used. Additionally, narcotic medications such as oxycodone if necessary, nonnarcotic medications such as Tylenol and non-steroidal anti-inflammatory medications as indicated.
- Patients with fevers, chills, nausea, vomiting, or other systemic symptoms will be directed to their local emergency room, urgent care, urologist's office, or primary care physician as appropriate for further evaluation and management.

#### 7.4 Duration of Therapy

Therapy is administered weekly for a total of 6 weeks. If a patient's therapy is deferred for one week due to infection, gross hematuria, symptoms, or other reasons (e.g. travel, personal reasons why a patient may not attend a scheduled clinic visit, travel issues), patients will resume therapy the next week they are able to do so.

#### 7.5 Duration of Follow-Up

For the purposes of this study, symptom and adverse event evaluation as well as patient-reported outcomes will be collected weekly, including 1 week following completion of BCG therapy. From a bladder cancer standpoint, patients are followed on an ongoing basis, and will generally undergo a subsequent cystoscopy in clinic or the OR for the purpose bladder cancer surveillance within 2-6 weeks of completion of induction BCG to assess efficacy of the treatment and for bladder cancer response vs. persistence and/or progression. No imaging is indicated as per this protocol. However, patients with high risk NMIBC undergo annual CT scans for routine standard of care cancer staging.

#### 7.6 Dosing Delays/Dose Modifications

- A urine analysis will be performed prior to instillation. If bactiuria is present on high power field or >5 WBCs are present on high power field and/or gross hematuria is noted and/or the patient complains of acute cystitis symptoms (urinary urgency, frequency, dysuria), instillation is deferred and urine is sent for culture to confirm the presence of UTI and sensitivity to culture. Appropriate antibiotic therapy is prescribed per standard of care clinical practice. Findings are discussed with the prescribing clinician. Microscopic hematuria only or isolated WBCs in an otherwise asymptomatic patient do not preclude treatment.
- For patients reporting severe bladder pain, bladder spasms, urgency/frequency, in consultation with their primary urologist, the dose of BCG may be decreased to half-strength (25mg/50mL) as indicated.

#### 7.7 End of Treatment (EOT) Visit Schedule and Procedures

EOT Visits for all subjects who discontinue from the study will occur at least 7 days, but  $\leq$  30 days, after the last dose of intravesical therapy and prior to beginning other treatment. Procedures to be performed during the EOT Visit include:

- Physical Exam
- Vital Signs
- Performance Status
- Labs: urine analysis with reflex culture
- AE Assessment
- Patient Surveys: EORTC-QLQ-NMIBC-24, EORTC QLQ-C30
- Medication List
- List of complementary and alternative therapies

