## 9.0 SUBJECT DISCONTINUATION OF ACTIVE TREATMENT

Subjects may be removed from this study at any time at their discretion. Subjects may also be removed from this protocol if they develop any untoward side effects from the study treatment (acupuncture).

If a subject withdraws consent to participate in the study or aspects of the study, we will request permission to record survival data up to the protocol-described end of the subject follow-up period.. Documentation in the medical record should state that the subject is withdrawing from the study and what, if any, selected data the subject will permit the investigator to obtain.

If a subject withdraws from the study, they will not be replaced. Patients who withdraw or whom are removed from the study by their primary urologist (e.g. in whom their primary urologist determines it is not safe or indicated to proceed with BCG induction due to side effects, other comorbidities, lack of tolerance, or other patient-related concerns) will be surveyed to determine the reason for withdrawal. I.e. An explanation for discontinuing treatment is recorded for each subject discontinuing treatment on the appropriate CRF/eCRF. All subjects, irrespective of treatment status, will continue to be followed for survival. Treatment in this study must be discontinued for any of the following reasons:

- if the Sponsor decides to stop the study;
- at Investigator's discretion;
- at the subject's request;
- if the subject enrolls in a trial of another investigational agent;
- Grade 4 or life-threatening toxicity (See Section 11, Adverse Events) attributable to acupuncture;
- toxicity reactions of Grade 3 or higher, according to the grading in Appendix X - NAME Grading Scale
- pregnancy;
- development of severe BCG toxicity or side effects, e.g. BCG-sepsis, severe refractory BCG cystitis, that preclude the patient from being able to tolerate further BCG instillation.

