#### 14.2.2 Secondary Endpoints

1. BCG instillation adherence out of a possible planned six treatments (**successful adherence** defined as the number of successfully administered BCG instillations (of a possible 6 total)), **treatment interruptions** (defined as number of weeks that a BCG instillation was delayed), **weeks missed** (measured as any vs none, and total weeks that BCG was not administered of the planned 6 weekly induction doses of intravesical BCG), **intravesical BCG dwell times** (measured

in minutes), and **requirement for dose reductions** (measured as yes/no) between the acupuncture and control arms will be compared via t-test and chi-square as appropriate.

2. Responses of patients in the experimental and control arms to the EORTC QLQ-NMIBC-24(1) and EORTC QLQ-C30(2) symptom index will be compared via t-test at each time point.
3. **Median weekly pill counts** of medications prescribed for the management of BCG-related side effects, standardized by dosage across medication types, will be compared via Wilcoxon rank sum test.

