#### 14.3 Sample Size and Power

This study will have a sample size of 45 with 2:1 for treatment to control arm. The primary outcome is feasibility. This outcome is assessed through a mix of qualitative reports (trial recruitment, retention, protocol adherence, patient/provider feedback and evaluation of adverse events). For the qualitative reports there is no statistical testing, thus there is no formal power analysis. Based on prior experience we felt we needed at least 15 patients in each arm are to assess these factors quantitatively. For the patient survey, the two arms will be compared using t-test. For a trial designed with 90% power and two-sided 5% significance, we did the recommended pilot trial sample sizes per treatment arm of 15 for small standardized effect sizes (0.2) with continuous data(26). This sample size should also apply to continuous secondary endpoints. Extrapolating this reference point, we then doubled the treatment arm size in order assess some of the secondary endpoints within the treatment arm (e.g. responses of patients to the EORTC- QLQ-NMIBC-24 symptom index). Lastly, for a two-sample proportions test at 80% power and 5% significance, we calculated being able to observe a 0.4 difference between the 2 groups for binomial endpoints.

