#### **14.6 Indications for Stopping**

Patients participation will be terminated for the following indications:

- If they express a preference to no longer part in the study/personal preference.
- For major side effects or toxicities or complications associated with acupuncture resulting in patient request to not continue
- If the study investigators determine that it is no longer safe or feasible for a patient to continue to receive BCG or acupuncture due to progression of bladder cancer or other comorbid conditions.

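### Patients removed from the study when BCG is stopped for side effects drop out of the weekly EORTC comparisons, and their one end-of-treatment survey is assigned to no time point

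*Combined protocol and SAP*

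**What the plan says.** Four parts of the combined protocol and SAP bear on a patient who stops BCG early.

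- **Section 9.0** groups patients taken off by their urologist, including for side effects or lack of tolerance, with those who withdraw. They are asked the reason and are not replaced. The section adds: "All subjects, irrespective of treatment status, will continue to be followed for survival".
- **Section 7.7**: "EOT Visits for all subjects who discontinue from the study will occur at least 7 days", and at most 30 days, after the last intravesical dose. The visit includes each EORTC form once and a medication list, but not the weekly diary. It has no row in Section 8.1 and no column in Appendix D.
- **Section 14.6** opens "Patients participation will be terminated for the following indications". The list covers patient preference, major acupuncture complications that lead the patient to ask to stop, and an investigator's decision that BCG or acupuncture cannot go on because of disease progression or comorbidity.
- **Section 7.5** says patient-reported outcomes are collected weekly up to one week after BCG is completed. It is silent on patients who never complete it.

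Sections 3.3 and 8.1 place the weekly EORTC forms at the BCG visits. Section 3.3.2 compares them by week of treatment, 1 to 6, and Section 14.2.2 says that they "will be compared via t-test at each time point". The plan states no analysis set, no missing-data rule and no rule that gives the end-of-treatment survey a time point.

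**The concern.** The EORTC forms measure the bladder symptoms that can lead a urologist to stop BCG, so losing the patients who stop is unlikely to be random. Section 3.3.2 expects more acupuncture patients to finish BCG and expects the symptom benefit to grow over the six weeks. If that is right, the control arm loses more of its symptomatic patients at exactly the weeks where a difference is looked for, and a t-test on those who remain understates the benefit. The Synopsis says the secondary data will inform power calculations for a Phase III trial, so a distorted late-week difference would carry forward. The weekly pill-count comparison has the same gap, because the diary is not part of the end-of-treatment visit.

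**Working it through.** **1. The path of a BCG stopper.** Section 9.0 removes the patient from the study. Section 7.7 gives one survey. The remaining weekly forms sit at BCG visits that no longer take place. Section 7.5 could be read as continuing weekly collection, but it ends at completion of BCG, which this patient does not reach. Sections 7.5, 7.7, 9.0 and 14.6 therefore do not give one answer, and must be reconciled.

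**2. Where the end-of-treatment survey falls.** On schedule, dose k is on day 7k − 6, so the survey window is day 7k + 1 to day 7k + 24. Week w (1 to 6) is day 7w − 6 ± 7. Week 7 is read as day 43 ± 14, that is, days 29–57.
- k = 1: days 8–31, overlapping the windows of Weeks 2, 3, 4, 5, 6 and 7.
- k = 5: days 36–59, overlapping the windows of Weeks 6 and 7.

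The survey can thus fall in two to six scheduled windows, and nothing says which one applies.

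**3. The plan's own figures.** "This study will have a sample size of 45 with 2:1 for treatment to control arm", so 30 and 15. "for a two-sample proportions test at 80% power and 5% significance", the plan states: "we calculated being able to observe a 0.4 difference between the 2 groups for binomial endpoints". With an assumed control rate of 0.10 against 0.50, the pooled rate is (1.5 + 15)/45 = 0.367. The null SE is √(0.367 × 0.633 × (1/15 + 1/30)) = 0.152, and the alternative SE is √(0.09/15 + 0.25/30) = 0.120. Then z = (0.4 − 1.96 × 0.152)/0.120 ≈ 0.85, and power is 80.1%. The 0.4 reproduces at that control rate, which is itself not stated. The sample size section has no stopping rate and no dropout allowance, so the bias below rests on assumed rates. Section 2.1's figure of about 40% is for interruptions, not stops.

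**4. Bias among those who remain.** Let scores be normal with SD 1, higher being worse. Let the tendency to stop correlate ρ with the score, and let a fraction p stop. With z_p the upper-p normal quantile, the mean score of those who remain is −ρ φ(z_p)/(1 − p). At ρ = 1 this is −0.195 (p = 10%), −0.350 (20%) and −0.644 (40%). With no true difference, acupuncture minus control among those who remain is:

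| Stopping, control vs acupuncture | ρ = 0.3 | ρ = 0.5 | ρ = 1 |
|---|---|---|---|
| 20% vs 10% | 0.046 | 0.077 | 0.155 |
| 40% vs 20% | 0.088 | 0.147 | 0.294 |

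For example, 0.3 × (0.350 − 0.195) = 0.046. Positive values make acupuncture look worse.

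With an assumed true benefit of −0.5 SD, a common stopping threshold and 20% of controls stopping, the observed difference is −0.45 at ρ = 0.5 and −0.33 at ρ = 1.

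**5. Precision.** The smallest effect detectable with 80% power (two-sided 5%, noncentral t) is 0.91 SD at 15/30. It is 1.00 SD at 12/27 (20% and 10% lost) and 1.13 SD at 9/24 (40% and 20% lost).

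**The case against.** The other side has real points, and several narrow the concern.

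- A reader might infer that anyone who stops BCG or acupuncture is terminated under Section 14.6. The text does not support that. Its investigator criterion is limited to progression or comorbidity, and its acupuncture criterion needs a patient request. A patient who stops only acupuncture and stays on BCG is not clearly removed, since Section 14.2.1 defines adherence and retention separately. Patients who are deferred or dose-reduced (Sections 7.4 and 7.6) stay in. The point concerns BCG stoppers under Section 9.0.
- A reader might infer that stoppers are followed only for survival. Section 9.0 promises survival follow-up without excluding anything else, and Section 7.5 speaks of weekly collection. This is a conflict between sections, not a clear end to follow-up.
- A reader might infer that the end-of-treatment survey cannot match any time point. It can, and a completer's Week 7 survey may itself come up to 21 days after dose 6 (day 57 − day 36). The survey is unassigned, not unusable.
- The direction is not fixed. Equal stopping rates in the two arms remove the shift in step 4's no-difference case, and more stopping in the acupuncture arm reverses it. Section 3.3.2 expects symptoms to build with each dose, so they may ease once BCG stops. Stoppers' later scores could then be better than those of patients still on BCG.
- The size is modest. The standard error of a weekly difference is √(1/30 + 1/15) = 0.32 SD, and these are secondary endpoints in a feasibility trial.

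All of this stands. None of it supplies the missing rule: Section 9.0 still removes BCG stoppers, and the analysis still has no place for them.

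**Conclusion.** The concern holds for patients whose BCG is stopped for side effects or intolerance. Followed as written, Sections 9.0 and 7.7 leave them with one survey that has no time point, and the weekly t-tests proceed without them. If more control patients stop and stoppers would have scored worse, the late-week comparison is biased against acupuncture. The amount cannot be fixed from the documents. At an assumed 20% versus 10% it is about 0.05 SD at correlation 0.3. The 0.15 SD at correlation 1 is a ceiling for those rates, because it makes the worst scorers exactly the ones who stop. The 0.29 SD for 40% versus 20% is likewise a ceiling under assumed rates, and should not be read as an expected bias. The harm is to the between-arm estimates meant for the next trial. The change is worth making because it is cheap.

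**What to change.** 1. In Sections 7.7, 9.0 and 14.6, separate stopping treatment from withdrawing from data collection, and bring Section 7.5 into line. No rule on when treatment stops needs to change.
2. Continue the weekly EORTC forms and medication diary by phone, email or mail through Week 7, unless the patient withdraws consent to data collection. Phone access is already an inclusion criterion (Section 5.1.4), and Section 3.3 already uses remote contact for baseline data and void times.
3. Assign every survey, including the end-of-treatment one, to a time point by calendar week from randomization or from the first planned BCG date.
4. Replace the weekly complete-case t-tests with a longitudinal mixed model of all randomized patients, adjusted for baseline. State that scores recorded after BCG stops are included. The model assumes that missing scores are explained by the observed data, so it does not by itself cure symptom-driven dropout. Add a simple sensitivity analysis, such as shifting the missing scores of stoppers by a range of amounts in each arm.

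The cost is protocol wording, a few remote surveys per stopper and modest coordinator time, with no extra clinic visits. The comparison will then mix on-BCG and off-BCG scores, which the report should say.
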